May 30, 2023

Effect of Flaxseed as a Treatment for Adults With Type 2 Diabetes Mellitus in Mexico

-CEI-04/2023-

**Study Protocol and Informed
Consent Form**

UNDER THE LEADERSHIP OF: DR. [name]

University of the Southern Sierra

University of the Southern Sierra

Effect of flaxseed consumption as a treatment for adults with type 2 Diabetes Mellitus in Oaxaca de Juarez, Oaxaca.

I. PRESENTATION OF THE PROTOCOL OR RESEARCH PROJECT

1. Summary of the study

Introduction: Type 2 Diabetes Mellitus represents one of the most important health emergencies of this century. It is estimated that by 2045 there will be 700 million people living with diabetes. Flaxseed is a food that is characterized by its nutritional properties, highlighting its content of alpha linoleic acid, flax lignans, digluc- secoisolariciresinol cosides. The latter have antioxidant, hypolipidemic and hypoglycemic effects, which makes it an excellent option as a functional treatment for type 2 diabetes.

Material and Method: Randomized clinical trial. The sample will be recruited by self-selection.

The control group will be given a nutritional education talk using the healthy eating plate and the group intervention you will be prescribed flaxseed supplementation (16 gr of flaxseed/day for three months) and also a talk of nutritional education using the healthy eating plate. A clinical history will be applied for the variables age, gender, occupation and marital status, duration of the disease, type of current diabetes treatment, control and comorbidities, weight, height and biochemical parameters glucose, glycosylated hemoglobin, total cholesterol, triglycerides, LDL cholesterol, and HDL cholesterol of each participant, at the beginning and at the end of the study.

Scientific/Practical Relevance: The use of flaxseed as a functional food for the treatment of type 2 diabetes is It has been used in different populations with success. However, in the state of Oaxaca its effectiveness has not been tested despite having this food available. If the results are positive, this food can be offered as a therapeutic alternative instead of or in combination with its pharmacological treatment, improving the results. This is important because the prevalence of this disease in the state is increasing.

Keywords: Type 2 Diabetes Mellitus, treatment, functional food, Flaxseed.

Expected start and completion dates of the study.

Start: October 2023

Study completion: March 2025

2. Objectives

General

- To assess the adjuvant effects of flaxseed consumption (16 g of flaxseed per day/3 months) on

Biochemical factors (glucose, glycosylated hemoglobin, total cholesterol, triglycerides, LDL cholesterol and cholesterolHDL) of adult patients (30 to 70 years) with type 2 diabetes mellitus, who attend the Nutrition outpatient clinic from the Regional Hospital of Oaxaca.

Specific Objectives

1. Describe the sociodemographic variables (age, sex, occupation, marital status) of adult patients (30 to 70 years) who suffer from type 2 diabetes, who attend the Nutrition outpatient clinic at the Regional Hospital from Oaxaca.
2. Describe the clinical characteristics (time of evolution of the disease, type of treatment, control and comor-bilities), of adult patients (30 to 70 years) who suffer from type 2 diabetes, who attend the outpatient clinic of Nutrition at the Regional Hospital of Oaxaca.
3. Assess the anthropometric variables (weight and height) of adult patients (30 to 70 years) who suffer from diabetes type 2, who attend the Nutrition outpatient clinic at the Regional Hospital in Oaxaca.
4. Evaluate the biochemical parameters (glucose, glycosylated hemoglobin, total cholesterol, triglycerides, LDL cholesterol and HDL cholesterol) of adult patients (30 to 70 years) suffering from type 2 diabetes, who attend the Nutrition outpatient clinic of the Regional Hospital of Oaxaca, prior to the consumption of flaxseed and three months after regular consumption of flaxseed.

5. Apply a nutritional intervention to two groups: Group A) Teaching the healthy eating plate and Group B) Teaching healthy eating dishes and indicating flaxseed consumption.
6. Evaluate the effect of flaxseed consumption on biochemical markers (glucose, glycosylated hemoglobin, Total cholesterol, triglycerides, LDL cholesterol and HDL cholesterol of adult patients (30 to 70 years) suffering from type 2 diabetes, who attend the Nutrition outpatient clinic at the Regional Hospital in Oaxaca.
7. Analyze the most effective possible combinations (pharmacological + non-pharmacological) for the treatment of Adult patients (30 to 70 years) who suffer from type 2 diabetes, who attend the Nutrition outpatient clinic at the Regional Hospital of Oaxaca.

4. Justification

Type 2 Diabetes Mellitus represents one of the most important health emergencies of this century. It is estimated that in 2019, there were already 463 million people with diabetes mellitus worldwide and this figure may increase to 578 million by 2030 and to 700 million by 2045. A state of hyperglycemia is associated with acute and chronic complications, in both cases affecting the cardiovascular system, mainly the blood vessels and consequently to the entire organism, but mainly to the eyes, kidneys, arteriovelocity systems and peripheral nerves. Although it is known that insulin resistance is reversible and that diabetes mellitus type 2 is controllable with a change towards a healthy lifestyle, the population ignores these recommendations and continue with their unhealthy habits. Thus, the number of patients continues to grow exponentially, which leads to an increase in economic expenditure in terms of health. This is why non-pharmacological measures are sought that favor the reduction of glycemia in patients with Diabetes Mellitus where the consumption of functional foods is a good alternative for the treatment of this chronic disease (Tinajero et al., 2021; Wu et al., 2014). Flaxseed is a food characterized by its nutritional properties, highlighting its content of alpha linoleic acid, flax lignans, and secoisolariciresinol diglucosides. The latter have antioxidant, lipid-lowering and hypoglycemic effects, which makes it an excellent option as a dietary supplement for treatment of type 2 diabetes (Parikh et al., 2019).

Some studies have been conducted with flaxseed supplementation. In a randomized cross-sectional study conducted by Tharwat et al., in 2017, evaluated 90 patients with type 2 Diabetes Mellitus with a range of 5 to 7 years of diagnosis

that they received oral hypoglycemic agents (metformin 500 mg) 3 times a day, having an age range between 35 and 45 years old. They divided the population into 3 groups:

Group 1 selected 30 patients with a calculated diet to 1350kcal (in the form of 50% carbohydrates, 30% fat and 20% protein) without flaxseed supplementation.

Group 2 included 30 patients with the same diet, but adding linseed oil for 6 days a week in an amount of 13g/day. And in group 3, 30 patients were included in the same dietary regimen that group 1, adding flaxseed flour to their diet for 6 days a week, providing 32g of flaxseed per day. They concluded that in the 3 groups there was a reduction in blood glucose, however the decrease in glucose in Fasting reported by group 3 had better target figure achievements (Tharwat., 2017).

In a systemic review in 2018 Mohammadi et al, evaluated 25 randomized clinical trials, presenting a significant association between flaxseed supplementation and a reduction in blood glucose. It is worth mentioning that this relationship was more significant in the groups in trials that used ground flaxseed and reported an administration between 4 to 14 grams. (Mohammad., et al, 2018)

Hasaniani et al in 2019 conducted a randomized, controlled clinical trial with 57 patients with Diabetes Mellitus type 2. He divided his population into 2 groups. One group was prescribed 200g of natural yogurt in their diet and the other. Another group was also prescribed 200g natural yogurt with 30g of flaxseed added for 8 weeks documented a significant reduction in hemoglobin A1c ($p=0.001$) compared to the control group (Ha-saniani, 2019). In another study, Nowak concluded that regular consumption of flax seed improves the lipid profile by reducing triglycerides and total cholesterol and increasing HDL cholesterol (Nowak & Jeziorek., 2023)

5. Design of the research methodology.

Randomized clinical trial (case-control).

The sample will be recruited by self-selection.

The total number of recruited participants will be divided into two groups (A and B).

The control group will be given a talk nutritional education using the healthy eating plate and the intervention group will be instructed on supplementation with flaxseed (16 gr of flaxseed/day for three months) and also a nutritional education talk using the plate of good eating.

Once they sign the legal informed consent for participation, a clinical history will be applied where

Sociodemographic variables such as age, sex, occupation and marital status will be

asked. Clinical characteristics such as time since the disease has been on the disease, type of current diabetes treatment, control and comorbidities will also be asked. These variables will be collected at the beginning of the research and only once during the study.

The nutritionist will take the participant's weight and height and record them at the beginning and end of the study.

Specialized nurses will take 5 milliliters of blood in the clinical laboratory area of the Regional Hospital

from the of Oaxaca and a clinical chemist professional will assess the biochemical parameters glucose, hemoglobin glycosylated, total cholesterol, triglycerides, LDL cholesterol and HDL cholesterol of each participant, at the beginning and at the end of the study (after three months of intervention, consuming 16 g of flaxseed/day).

The effect of flaxseed consumption on biochemical markers (glucose, hemoglobin) will subsequently be evaluated.

glycosylated, total cholesterol, triglycerides, LDL cholesterol and HDL cholesterol and the possible combinations will be analyzed (pharmacological + non-pharmacological) most effective for the treatment of type 2 diabetes.

6. Selection criteria and description of participants.

Selection criteria

Patients living with type 2 Diabetes Mellitus and who come with fasting blood glucose greater than 140 and hemoglobin glycosylated greater than 6.5%, who are beneficiaries who attend the Nutrition outpatient clinic of the Hospital-Regional "Presidente Benito Juárez" diagnosed at most one year ago and who agree to participate in the study, age between 45 and 65 years with regular attendance at the outpatient clinic, minimum of 3 consecutive months.

7. Methods of selection and inclusion of participants in the study.

Phase 1. Sample recruitment.

The convenience sample will be recruited by self-selection: patients who attend the nutrition outpatient clinic that meet the inclusion criteria, they will be invited to participate in the study. After giving them all information, those who wish to participate will sign the legal informed consent for participation.

Phase 2. Case randomization procedure.

Patients who sign the informed consent will be assigned a group according to the following: in the case

If you have an even number in your file, you will be part of the control group (A), and if you have an odd number, you will be part of intervention group B.

Group A.

They will be given verbal instructions to continue with the treatment established by the treating physician, and they will be provided with nutritional guidance with the help of the healthy eating plate.

Group B.

They will be given verbal instructions to continue with the treatment established by the treating physician, they will be given nutritional guidance with the help of the healthy eating plate and they will be provided with a pamphlet with the instructions. written and photographed on how to consume flaxseed and its benefits.

Phase 3.

Administration of flaxseed

Researchers will purchase, package, and provide flaxseed powder to members of group B. Flaxseed will be delivered in packages with 16 gr of ground flaxseed each, which will be given to patients for their daily consumption (a tablespoon of 8

gr of flaxseed in the morning snack and 8 gr of flaxseed in the afternoon snack)

(late). You will be provided with brochures with images explaining how to consume it and how the glass should look when finished. Various forms of consumption of the powder will also be provided to avoid getting bored with the taste and consistency. from dust.

Phase 4.

Surveillance and monitoring.

Daily contact will be maintained with participants via WhatsApp in order to remind them to take flaxseed.

and also to find out if they have any adverse symptoms (abdominal distension, flatulence, gas, diarrhea, etc.), as well as to resolve doubts and ask if they should start taking some vitamins, minerals or medications.

Both groups will be given a 24-hour recall and a food frequency questionnaire. every 15 days. The food consumption of both groups will be analyzed according to its nutritional content (energy, macro and micronutrients) and each nutrient will be used as a nutritional variable that can influence the control of the biochemical markers.

Phase 5.

Data analysis.

Statistical analysis will be performed using the IBM SPSS Statistics program version 24, in which it will be performed descriptive statistics and for group comparisons different tests will be performed depending on the nature of the variables. The comparison between the values measured at the beginning and the values measured after 3 months in each group will be performed using the paired t test and will be

considered statistically significant when $p < 0.05$.

Inclusion criteria:

- ÿ Patients entitled to who attend the “Presidente” Regional Nutrition outpatient clinic Benito Juárez” diagnosed at most one year ago and who agree to participate in the study by signing the informed consent.
- ÿ Patients diagnosed with uncontrolled Diabetes Mellitus evidenced by biochemical markers, den-
within a maximum of 1 month of validity, (fasting blood glucose greater than 140 and glycosylated hemoglobin greater than (6.5%).
- ÿ Patients with regular attendance at the outpatient clinic for at least 3 consecutive months.

Exclusion criteria:

- ÿ Patients diagnosed with chronic kidney disease undergoing renal function replacement therapy.
- ÿ Patients who already consume enough fiber and omega 3, as evidenced by the application of a reminder of 24 hours and a food frequency questionnaire.
- ÿ Pregnant or
breastfeeding women.
- ÿ Patients in
menopause.
- ÿ Patients with glucose disorders secondary to autoimmune diabetes, thyroid diseases or insulin-producing tumors.
- ÿ Patients with a medical history of poor drug adherence.
- ÿ Patients with adequate glycemic control evidenced by clinical laboratory tests for at least 2 months.
- ÿ Patients who cannot read or write.

ÿ Patients who do not have a means of contact for follow-up.

Elimination criteria:

ÿ Patients who do not agree to participate in the study. ÿ Data collection instrument with incomplete items.

ÿ People who voluntarily withdraw from the study at any time. ÿ If the patient has surgery during the study.

ÿ Patient who during the study begins to consume any type of supplement (vitamins, minerals, omega 3).

ÿ Patient who stops consuming flaxseed during the study.

8. Experience of the principal investigator and co-investigators in this type of research.

(maximum)

The principal investigator has participated in different research projects in the area, both as a collaborator and as principal investigator:

-Collaborating researcher. Faculty of Nutrition. Universidad Veracruzana. **“Evaluation of waist circumference in fifth period students of proposal 3 and 4 as a risk factor for developing metabolic syndrome”**. Faculty of Nutrition. Xalapa, Universidad Veracruzana, Mexico. 2010. SATISFACTORILY COMPLETED

-Collaborating researcher. Cooperation with the Coordination of the Master's Degree in Food and Nutritional Security.

“Influence of maternal nutrition on the programming of fetal adipose tissue development”. Faculty of Nutrition. Universidad Veracruzana. 2011. SATISFACTORILY COMPLETED

-Collaborating Researcher. **“Influence of physical activity on biochemical and vascular factors determining endothelial dysfunction in postmenopausal women”**. Sant Joan de Reus University Hospital, Tarragona, Spain, 2012. SATISFACTORY COMPLETED

-Collaborating researcher. INCOS Project (Community Health Intervention), **“Effect of a community intervention in school children, considering nutritional and cognitive status”**. Ccorca District, Cusco, Peru.

NUTRISAM Research Group of the Rovira I Virgili University, Spain. 2013. Project Grant from the Rovira i Virgili University, Spain. SATISFACTORILY COMPLETED

-Principal investigator. PESA-T Project (Health Assessment Project) **“Nutritional Transition State of the city of Cuzco, Peru”**. NUTRISAM Research Group. Project Grant from the Rovira I Virgili University, Spain. March-September 2014. SATISFACTORILY COMPLETED

-Principal investigator of the project **“EMOTIONAL NUTRITIONAL STATUS IN FOOD SAFETY AND HEALTH”**

THE OAXACAN POPULATION DURING CONFINEMENT DUE TO THE SARS-COV-2 VI-RUS”, registered at the Nutrition Institute of the University of the Sierra Sur (UNSI) with folio CEI-09A / 2020. In progress

-Principal investigator of the project **“NUTRITIONAL STATUS, FOOD CONSUMPTION AND INTAKE NUTRITIONAL IN CONFIRMED AND RECOVERED CASES BY SARS-Cov-2 IN THE STATE OF OAXACA, MEXICO”**, registered at the Nutrition Institute of the University of the Sierra Sur (UNSI) with the folio INUT/NC/2021/01/270821. In progress

-Co-technical manager of the Project **“Molecular epidemiology of drug use and comorbidities in Mexican population, as well as its repercussions on the Mexican legal framework”**, registered in the Institute of Nutrition from the University of the Sierra Sur. INUT/BMBCS/05/2020. In progress

9. Potential risks and benefits for participants and for society, as well as compensation for those involved participants.

According to the general health law on health research in its article 17, this is considered Low risk study because biochemical tests will be taken and this could cause the participant pain in the extraction area, and you may also experience some symptoms from taking flaxseed such as constipation, diarrhea, or gastrointestinal upset.

The participant will not receive financial compensation, but the results of the study will be published and disseminated. Based on the results of the studies, participants may potentially receive the benefit of improved controlling your type 2 diabetes.

10. Management of potential risks for participants.

To minimize risks, researchers will be in daily contact with participants to warn them any damage to health and to know if any gastrointestinal reaction or even allergic reaction occurs, this in order to be able to tell you what to do or even stop the study if necessary. In case the discomfort persists, the responsibility of the research team will be guaranteed to provide immediate nutritional care to the participant (as established in articles 18 and 19 of the Regulations) of the General Health Law on Health Research).

The risk management process will be as follows:

1. Identify risk	The patient will be monitored in case of any health problems caused by flaxseed.
2. Analyze	The symptom will be analyzed.
3. Prioritize risk	It will be verified that your health is not compromised.
4. Control the risk	If the symptom is controllable, the treatment will continue and if it is not, the patient can withdraw.

of the study. If the patient presents any

stress problems due to the administration
tion is withdrawn from the study.

11. Procedure by which consent to participate in the study will be obtained.

- Participants who meet the inclusion criteria will be recruited in the nutrition outpatient clinic from the Regional Hospital of Oaxaca.
- You will be provided with detailed information about the study and will be provided with written informed consent/legal participation document (ANNEX 1)
- You will be given time to proceed with the reading of the document and you will have time in case the participant has doubts or questions about the study.

12. Management of confidentiality of information.

Upon entering the study, each participant will be registered with a number by which they will be addressed throughout the study. All data will be treated anonymously.

13. Conflicts of interest.

There is no conflict of interest

14. Bibliography

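### Changes in diabetes drugs over the 3 months are not reliably captured, and Objective 7 and the summary's replacement claim go beyond the add-on comparison the trial makes

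*Protocol*

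**What the plan says.** **Recording of drugs.** Section 5 of the Protocol puts type of current diabetes treatment in the clinical history taken after consent, and states: "These variables will be collected at the beginning of the research and only once during the study". The same section has weight, height and the laboratory values taken at the start and again at the end.

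**Follow-up contact.** Section 7, Phase 4 says: "Daily contact will be maintained with participants via WhatsApp in order to remind them to take flaxseed". The contact also covers adverse symptoms and asks about starting vitamins, minerals or medications. Separately, a 24-hour recall and a food frequency questionnaire are scheduled every 15 days, expressly for both groups. The elimination criteria remove a patient who begins a supplement; they do not mention a change in diabetes drugs.

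**Background treatment.** Section 7 gives group A this instruction: "They will be given verbal instructions to continue with the treatment established by the treating physician, and they will be provided" with nutritional guidance. Group B receives the same: "They will be given verbal instructions to continue with the treatment established by the treating physician, they will be given nutritional guidance", plus the flaxseed.

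**Aims and intended conclusions.** The general objective in section 2 is "To assess the adjuvant effects of flaxseed consumption". Specific Objective 7 is to "Analyze the most effective possible combinations (pharmacological + non-pharmacological) for the treatment of" these patients, and section 5 repeats that "the possible combinations will be analyzed (pharmacological + non-pharmacological) most effective for the treatment of type 2 diabetes". The summary in section 1 says that, if results are positive, "this food can be offered as a therapeutic alternative instead of or in combination with its pharmacological treatment".

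**The concern.** Three related matters are at stake.

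1. **Data capture.** Patients enter with uncontrolled diabetes, were diagnosed within the past year and attend clinic regularly, so drug changes within 3 months are plausible. There is no placebo, so participants know whether they take flaxseed, and that knowledge could affect whether their drugs are changed. If starts, stops or dose changes differ between arms, a difference in glucose or HbA1c mixes flaxseed with drugs, and the planned data could not reliably show it. Data that were not collected cannot be supplied by a later analysis plan.

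2. **Objective 7.** Only flaxseed versus no flaxseed is assigned. The drug regimen is the treating physician's choice, so comparing patients across drug combinations compares patients who were prescribed differently for clinical reasons.

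3. **Replacement.** Both arms continue their drugs. A positive result would say something about adding flaxseed and nothing about using it in place of treatment.

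**Working it through.** The Protocol gives no sample size, effect size, standard deviation or rate of drug change, so there is no stated figure to reproduce. The first and last steps set the text side by side. Steps 2 to 4 use inputs marked as assumed.

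**Step 1. What is recorded, when, and for whom**

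| Item | Baseline | Follow-up | Month 3 | Both arms stated? |
|---|---|---|---|---|
| Weight, height, laboratory values | yes | – | yes | yes (participants generally) |
| Diet recall and food frequency | – | every 15 days | – | yes, expressly |
| Type of diabetes treatment | yes, once | no scheduled record | none described | baseline only |
| Starting a medication | – | asked by WhatsApp; no record specified | – | not clear |
| Drug dose change or stop | – | not named | not named | – |

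Scheduled diet contacts: 90 days / 15 days = 6 per participant. Diabetes treatment is formally recorded at none of the 6.

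**Step 2. Possible bias in the between-arm HbA1c difference (illustration)**

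Bias = (difference between arms in the share with drug intensification) × (mean HbA1c effect of intensification).

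- Assumed low end: 0.10 × 0.5 = 0.05 points
- Assumed high end: 0.20 × 1.0 = 0.20 points
- With a 30-point difference instead: 0.30 × 1.0 = 0.30 points

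The direction is unknown. More intensification in the control arm would hide a flaxseed effect; more in the flaxseed arm would inflate it.

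**Step 3. Precision of an exploratory analysis by baseline treatment type**

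Let N be the total number of patients, allocated 1:1, s the outcome standard deviation, and p the share in one of two treatment types.

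- Var(flaxseed minus control, overall) = 4s²/N
- Var(difference in flaxseed effect between types) = 4s²/(Np) + 4s²/(N(1−p)) = (4s²/N) / (p(1−p))
- Variance ratio = 1/(p(1−p))

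| Assumed split | Variance ratio | Standard error ratio |
|---|---|---|
| 50/50 | 1/0.25 = 4 | 2.0 |
| 80/20 | 1/0.16 = 6.25 | 2.5 |

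Equal precision therefore needs 4 to 6.25 times as many patients, with only two treatment types.

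**Step 4. The same point as sample size**

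Assumptions: two-sided 5%, 80% power, 1:1 allocation, normal approximation, two equal strata. With z = 1.960 + 0.842, n per arm is 2(z/d)² for the main effect and 8(z/d)² for an interaction of the same standardized size d.

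| Assumed d | Main effect, per arm | Interaction, per arm |
|---|---|---|
| 0.3 | 175 | 698 |
| 0.5 | 63 | 252 |
| 0.8 | 25 | 99 |

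**Step 5. Aims against design**

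- Assigned contrast: flaxseed plus continued treatment versus continued treatment. This matches the adjuvant general objective.
- Drug combinations assigned by the study: none. Objective 7 and the matching sentence in section 5 are not matched by the design.
- Arms in which flaxseed replaces drugs: 0 of 2. The summary's replacement wording is not matched by the design.

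**The case against.** **Capture may be better than it looks.** Contact is daily, roughly 90 occasions, and medications are mentioned, so counting only the 6 diet contacts understates the opportunity to learn of a change. Phase 4 speaks of participants, whereas Phase 3 names group B when only that group is meant; section 10 also has daily contact with participants without limit, and patients without a means of contact are excluded from either arm. Removing patients who start supplements requires that such information be obtained. Both arms are told to continue treatment and patients with a history of poor drug adherence are excluded, which should limit changes. The text reads as a translation, so too much should not hang on one verb.

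These points rule out saying that drug changes are never captured. They do not supply a month-3 treatment record, a question on dose or stopping, or a stated record of the answers. Coverage of the control group stays unclear, since the contact's first purpose is a reminder to take a product that group does not receive.

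**Effect of assignment.** If later drug changes count as part of the strategy, the between-arm difference still estimates the effect of being assigned to flaxseed advice and supply. That is correct. Attributing the difference to flaxseed itself is a further step, and in an open trial it needs drug changes to be known by arm.

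**Wording.** Ranking is not the Protocol's word, an exploratory analysis by baseline treatment is feasible, and the replacement phrase is conditional and appears once, beside the add-on alternative. All true, which is why narrowing is enough. But identifying which combinations are most effective does imply comparing them, and objectives and intended conclusions belong to the Protocol.

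**Size.** The HbA1c shift rests wholly on assumed inputs. It shows what is possible and does not estimate what will happen.

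**Conclusion.** The concern holds. As written, the trial formally records diabetes treatment once, and the follow-up enquiry is too incomplete to show reliably whether drug changes differ between arms. The size of any resulting bias cannot be taken from the Protocol; 0.05 to 0.20 HbA1c points follows from the assumed 10 to 20 point imbalance and 0.5 to 1.0 point effect.

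The design supports a conclusion about flaxseed added to continued treatment. It does not support identifying the most effective drug plus non-drug combinations, and it has no arm that tests replacement. An analysis of the flaxseed effect by baseline treatment type can be done, but with a standard error 2.0 to 2.5 times that of the main comparison (two types, assumed splits of 50/50 to 80/20) it can only be exploratory. The change should be made, and the data-capture part matters most because it cannot be repaired reliably after follow-up. The two wording points are lesser, but they govern what the trial would claim.

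**What to change.** - **Record drugs in both arms.** At the 15-day contacts and at month 3, note each diabetes drug, its dose, and any start, stop or dose change since the last contact. Report changes by arm alongside the HbA1c and glucose results.
- **Restate Objective 7 and the matching sentence in section 5** as an exploratory analysis of whether the flaxseed-minus-control difference varies by baseline treatment type (group by treatment-type interaction), without ordering combinations by effectiveness.
- **Reconcile the summary in section 1 with the general objective in section 2**, so that stated conclusions are limited to the comparison made: flaxseed added to continued treatment.

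Cost: one short new medication item about 6 times per participant beside the diet questionnaires, which do not now cover drugs, and once at month 3, plus three wording changes. The price is a narrower claim.

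### Allocation by odd or even file number is not randomisation, and the arm can be read before a patient is invited, so selection bias can enter a trial labelled randomised

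*Protocol*

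**What the plan says.** The Material and Method paragraph of the protocol's section 1 describes the study as: "Randomized clinical trial. The sample will be recruited by self-selection". Section 5 repeats the label with a second, incompatible one added in brackets: "Randomized clinical trial (case-control").

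Section 7 gives the procedure. In Phase 1, clinic patients who meet the criteria are invited: "The convenience sample will be recruited by self-selection". The next step is headed "Phase 2. Case randomization procedure" and begins: "Patients who sign the informed consent will be assigned a group according to the following". The rule for the control arm is "If you have an even number in your file, you will be part of the control group (A"). Its counterpart for the flaxseed arm reads "if you have an odd number, you will be part of intervention group B".

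The inclusion criteria, also in section 7, require "Patients with regular attendance at the outpatient clinic for at least 3 consecutive months". Section 12 mentions a different number, given on entry to the study to identify the participant. It is not called a file number and is not linked to allocation. The protocol describes no random sequence, no concealment and no blinding.

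**The concern.** The step presented as randomisation contains no element of chance. It is a fixed rule applied to a number that, for a regular clinic attender, should already be on the file. Whoever holds the file can know the arm before deciding whether to invite the patient, how to present the study, and how strictly to apply exclusions that have no threshold.

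Random, concealed allocation is what allows a difference between groups to be attributed to flaxseed. Without it, differences between the arms in motivation, diet or disease control can arise at entry and be mistaken for an effect on glucose, glycosylated haemoglobin or lipids. The protocol intends to draw a practical conclusion from a positive result: section 1 foresees offering flaxseed in place of, or together with, drug treatment. A later statistical analysis plan cannot repair this, because the protocol itself fixes the assignment rule.

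**Working it through.** The protocol states no figure on this point (no sample size, allocation ratio or expected effect), so there is nothing to reproduce. The check is mainly a comparison of passages.

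**1. Label against mechanism.** Sections 1 and 5 call the trial randomised, and section 7 heads Phase 2 as a randomisation procedure. The mechanism is: even number, control; odd number, flaxseed. Given the number, the probability of flaxseed is 0 or 1. Under a concealed 1:1 random sequence it is 0.5 for every patient at the time of invitation. The label and the mechanism do not agree.

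**2. When the arm can be known.** Phase 2 applies the rule after consent. Two readings of the number are possible:

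- *Clinic file number (plain reading).* Eligibility requires at least 3 consecutive months of regular attendance, so the file would exist before invitation. This is an inference; the protocol does not say it outright.
- *Study number given at entry (section 12).* If these numbers run in sequence, which is not stated, odd/even becomes strict alternation. Anyone who knows the last number issued knows the next arm.

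On the first reading, and on the second if numbers are sequential, the arm is foreseeable before enrolment. Assigning after consent does not conceal what can be read off beforehand.

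**3. Where foreknowledge can act.** Invitation is by convenience. Two exclusions in section 7 have no stated threshold: sufficient fibre and omega-3 intake, and a history of poor adherence to medication. Group B receives flaxseed powder and a pamphlet, and no placebo is described for group A, so the study is in effect open.

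**4. Illustration of size (assumed inputs).** Let prognosis be a standard normal score, and suppose a fraction f of the below-median half of one arm never enters, with no selection in the other arm. The mean of the upper half is √(2/π) = 0.798 and of the lower half −0.798. The remaining weights are 0.5 and 0.5(1 − f), so

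shift = 0.798 × [0.5 − 0.5(1 − f)] / (1 − 0.5f) = 0.798 × 0.5f / (1 − 0.5f).

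| f | Calculation | Shift (SD) |
|---|---|---|
| 0.2 | 0.798 × 0.10 / 0.90 | 0.089 |
| 0.3 | 0.798 × 0.15 / 0.85 | 0.141 |
| 0.5 | 0.798 × 0.25 / 0.75 | 0.266 |

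These shifts appear with a flaxseed effect of exactly zero. The values of f are assumptions; the protocol offers nothing from which to estimate them.

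**The case against.** The strongest reply is that prior knowledge of the arm is inferred. The protocol does not say which number is meant, when it is issued or who sees it, and it places assignment after consent. That is fair as to wording: the text supports that the arm can be known, not that staff will know it or act on it. It does not rescue the rule, which is deterministic under either reading and comes with no concealment.

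Other points carry some weight:

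- The main entry criteria are laboratory values (fasting glucose above 140, glycosylated haemoglobin above 6.5%), which leave little room for judgement. Discretion remains in the two exclusions without thresholds and, above all, in whom to invite.
- Convenience recruitment limits who the sample represents but does not by itself unbalance the arms; many properly randomised trials recruit this way. It matters here only because it gives free choice of invitees to people who can foresee the arm.
- Disease control and diet are recorded (baseline biochemistry, treatment type, repeated food recalls), so part of any imbalance could be adjusted for. Motivation and the decision to invite are not recorded, so adjustment would be incomplete.
- The parity rule does not fix the group sizes, but neither does simple randomisation; that is not a ground for objection.
- The illustration assumes one-sided selection by someone who judges prognosis well. Patients declining because of their arm would also need to know it before consent, which the protocol does not state. The figures show scale only.

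**Conclusion.** The concern holds. As written, the allocation is systematic (quasi-random), and the description as a randomised trial is not supported by the protocol's own procedure. For anyone who sees the number the assignment is fully predictable, against 50% under a concealed 1:1 sequence. This rests on the text of section 7 and, for foreknowledge before invitation, on the inference that a regular attender already has a file, or else on study numbers being sequential.

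The size of any bias cannot be derived from the protocol. The hypothetical range of 0.09 to 0.27 SD depends wholly on the assumed 20% to 50% selective loss from one arm. The claim is that bias can enter, not that it has. The defect must be corrected, because it removes the basis for a causal reading of the group comparison and cannot be fully repaired at analysis.

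**What to change.** Replace the odd/even rule in section 7, Phase 2, with a computer-generated 1:1 random sequence prepared and held by someone who does not recruit. Permuted blocks of randomly varying size are a good choice because they also keep the groups close in number, but any concealed random sequence cures the defect. Conceal it in sequentially numbered, opaque, sealed envelopes or an equivalent tool, and open each assignment only after eligibility, consent and the baseline blood sample are recorded. Remove the case-control label from section 5.

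The cost is one rewritten paragraph and a list with envelopes prepared once, with no added patients or visits. It does require one person outside recruitment, whose availability the protocol does not document.

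Section 1 planned the start for October 2023 and completion for March 2025. If patients have already been allocated by parity, new text cannot randomise them. In that case, describe the trial as quasi-randomised, report the numbers eligible, invited and consenting by file-number parity, adjust the between-group comparison for baseline values, and state that residual selection cannot be excluded.
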